5.2 Analysis

As defined in Section 3, data will be summarised using descriptive summary statistics only and no formal statistical testing will be carried out on any of the study endpoints.

5.3.1 Baseline characteristics

Baseline characteristics will be tabulated for all registered eligible patients using summary statistics overall and by dose.

5.3.2 Primary endpoints

The number of patients experiencing DLTs within the first cycle of KTD will be presented, with descriptive summaries of the specific DLTs observed. Summaries will be presented for each dose level. This data will be presented for patients registered to the dose escalation phase of the study only.

Further summaries of longer-term tolerability will also be presented for patients registered to the dose escalation phase to include the maximum toxicity grade experienced within the first three cycles of treatment, overall and by cycle. Individual listings of the toxicities, grade and cycle of all toxicities experienced within the first three cycles will be presented.

The number of patients experiencing any grade 3 or 4 CTCAE toxicity within all cycles of treatment will be summarised. This will be presented overall and by dose cohort, across all cycles as well as by each cycle.

5.3.2 Secondary endpoints

Safety and toxicity profiles for each cycle and cohort: data will be summarised descriptively, including the proportion of patients experiencing at least one SAE, the number of SAEs experienced per participant, and the number of SAEs experienced according to seriousness criteria, causality, and body system. Toxicity will be summarised according to CTCAE grades and will be summarised as the maximum grade toxicity experienced within each cycle, and overall.

The proportion of patients achieving at least a PR (clonal response) within 3m, at 3m, within 6m and at 6m and the proportion of patients achieving an amyloidotic organ response within 3m and 6m will be presented in tabulated form. Corresponding 90% and 95% confidence intervals will also be presented. Responses at 3 and 6 months will be broken down by response achieved, and by organ (for organ response).

Time to amyloidotic organ response and time to maximum response will be calculated using the Kaplan Meier method. Median time to amyloidotic organ response and median time to maximum response will be presented, with corresponding 95% confidence intervals.

The proportion and number of patients alive at 6 months and patients progression free at 6 months will be presented with corresponding 90% and 95% confidence intervals. If appropriate, Kaplan Meier curves for progression free survival may be explored.

Each patient will be assessed for their maximum clonal response; the number and proportion of participants in each response category within 6 cycles of treatment will be presented with corresponding 95% confidence intervals. Patients who do not achieve a maximum response will be summarised as, "no maximum response".

Feasibility of delivering treatment according to protocol schedule will be summarised descriptively to include the number of patients requiring dose delays and/or reductions, the number of patients withdrawing from treatment, and reasons for dose delays / reductions and withdrawals. Time on treatment and reasons for stopping treatment will also be presented. The number of doses missed will be summarised overall and by cycle.

6. Reporting and Dissemination of the Results

Final analysis will be carried out after the last participant's last data item.

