2.2 Secondary endpoints

- Clonal response rate within 3m, at 3m, within 6m and at 6m
- Amyloidotic organ response rate within 3m and 6m
- Time to amyloidotic organ response
- Number of deaths at 6 months
- Number of patients progression free at 6 months
- Maximum response
- Time to maximum response
- Number of patients withdrawing from treatment
- Number of patients experiencing dose delays, and compliance profile of KTD.
- Relative Dose intensity

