2.3.2 Secondary endpoints

Clonal response rate (based on paraprotein and FLCs) is defined as the proportion of patients who achieve at least a PR within 3 months, at 3 months, within 6 months and at 6 months after trial registration.

Amyloidotic organ response rate is defined as the proportion of patients who achieve organ response within 3

months and within 6 months of trial registration.

Time to Amyloidotic organ response is defined as the time from the dose allocation to first achieving organ response.

The number of patients experiencing dose delays will be defined as the number of patients experiencing delays in treatment with any of the study treatments.

KTD compliance: Patients will be regarded as compliant to treatment where treatment is received as per protocol until withdrawal from treatment and have no more than 1 dose omission of Carfilzomib, 5 of Thalidomide or 1 of Dexamethasone during each cycle.

Relative Dose intensity will be calculated as the percentage ratio between the received and planned dose intensities, where dose intensity is the cumulative dose divided by the duration of treatment.

3. Analysis Sets

Statistical analysis will be descriptive for all endpoints, and will be summarised overall and by dose cohort. All safety analyses will be based upon the safety analysis set; safety data from patients not included in this analysis set will be listed separately. All efficacy analyses will be based upon the per protocol set. Patients who do meet the criteria to be included in each of analysis sets will have the reasons for emission listed. A sensitivity analysis on the efficacy endpoints may be considered if the total number of patients in each of the analysis sets differs by more than 3 patients.

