5.1 General calculations

Unless otherwise stated, percentages will be calculated using the total number of patients in the appropriate population as the denominator (i.e. including all patients with missing data for that variable). All analyses will be carried out using SAS unless stated otherwise.

All percentages and means will be rounded to 1 decimal place and standard deviations to 2 decimal places. Values that are below the limit of detection and therefore non-quantifiable will be summarised using the limit of quantification value. For listings, if required, the non-quantifiable value would be reported as an inequality.

Summaries are divided into those participants treated at the recommended dose either during the dose escalation phase (prior to the identification of the recommended dose) or during the dose expansion phase (RD population), and all other participants treated during the dose escalation phase at dose levels other than the recommended dose (Non-RD population). The non-RD population will be split by dose level.

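### Six-month survival and progression-free rates are crude proportions with missing patients kept in the denominator, so each patient of unknown status lowers the rate as a death or progression would

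*SAP*

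**What the plan says.** SAP 5.3.2 (secondary endpoints) plans one presentation for both outcomes: "The proportion and number of patients alive at 6 months and patients progression free at 6 months will be presented", with 90% and 95% confidence intervals by an unnamed method. Protocol 19.4 has the same plan. SAP 5.1 sets the default that "percentages will be calculated using the total number of patients in the appropriate population as the denominator (i.e. including all patients with missing data" for the variable concerned, unless otherwise stated. Section 5.3.2 states nothing else for these two outcomes.

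The endpoints listed in SAP 2.2 and protocol 18.2 are "Number of deaths at 6 months" and "Number of patients progression free at 6 months". Neither SAP 2.3.2 nor protocol 18.3 derives them, defines being progression free at 6 months, or says how unknown status is classified.

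Kaplan-Meier is a firm commitment only elsewhere: "Time to amyloidotic organ response and time to maximum response will be calculated using the Kaplan Meier method". For progression it is optional: "If appropriate, Kaplan Meier curves for progression free survival may be explored". For overall survival it is not mentioned.

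SAP section 3 adds: "All efficacy analyses will be based upon the per protocol set".

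**The concern.** Counting a missing assessment as a failure is a familiar conservative convention for response. For survival it means that a patient last seen alive at month 3 and then out of contact contributes what a patient who died contributes. The proportion is then too low unless every such patient had in fact died or progressed, and its interval is centred on that low value.

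Unknown status can arise. Under protocol 14.2 a patient who declines further data has no more case report forms, and only safety data continue. Under protocol 13.2.2 an amyloidosis death more than 30 days after the last dose is not recorded as a serious adverse event, so it may not arrive by that route.

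Protocol 3.1 gives the expansion cohort the purpose of informing later trials. In a set this small, one or two patients move a 6-month rate visibly.

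**Working it through.** The plan gives no expected survival, precision or dropout for these endpoints, so there is no stated figure to reproduce.

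**Inputs**
- Recommended-dose (RD) cohort: 6 patients at the RD before expansion opens (protocol 8.1.3, Table 2) plus 20 in expansion (SAP 1.4), pooled under SAP 3.5. n = 6 + 20 = 26, before any per protocol exclusions.
- Deaths d and patients of unknown status l before 6 months: assumed and shown over a range, because the documents give neither.

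**Formulas**
- Planned figure: (n − d − l)/n.
- Kaplan-Meier, all losses before all deaths: (n − l − d)/(n − l).
- Kaplan-Meier, all deaths before all losses: (n − d)/n. This is also the proportion alive if every unknown patient is in fact alive.

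**Results for n = 26**

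| d | l | Planned figure | Kaplan-Meier range |
|---|---|---|---|
| 2 | 1 | 23/26 = 88.5% | 92.0% to 92.3% |
| 2 | 2 | 22/26 = 84.6% | 91.7% to 92.3% |
| 2 | 3 | 21/26 = 80.8% | 91.3% to 92.3% |
| 2 | 4 | 20/26 = 76.9% | 90.9% to 92.3% |
| 3 | 1 | 22/26 = 84.6% | 88.0% to 88.5% |
| 3 | 2 | 21/26 = 80.8% | 87.5% to 88.5% |
| 3 | 3 | 20/26 = 76.9% | 87.0% to 88.5% |
| 3 | 4 | 19/26 = 73.1% | 86.4% to 88.5% |

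In the case d = 3, l = 2, with deaths and losses alternating and a death first, Kaplan-Meier is (25/26)(23/24)(21/22) = 88.0%.

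**Cost per unknown patient.** It is 1/n: 1/26 = 3.8 points in the RD cohort, 1/20 = 5.0 points for 20 patients, and 1/38 = 2.6 points for the maximum total of 18 + 20. With l = 0 all formulas agree.

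**Interval.** Assuming exact (Clopper-Pearson) limits, d = 3 and l = 2 give 21/26 with a 95% interval of 60.6% to 93.4% and a 90% interval of 63.7% to 92.1%. If both unknown patients were alive, 23/26 has a 95% interval of 69.8% to 97.6%.

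The same arithmetic applies to the progression-free proportion, with d counting progressions and deaths.

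**The case against.** The strongest reply is that a proportion at a fixed time is legitimate over a short window that the plan intends to observe in full. Final analysis waits for 6 months of follow-up from registration (SAP 1.5). Patients who stop for non-response or progression still have a 6-month visit (protocol 9.4), those who discontinue for clinical reasons stay in follow-up (protocol 14.1.1), and missing data are chased (SAP 4.1). This stands: losses may be few or none.

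It also stands that SAP 5.1 sets a denominator and does not declare anyone dead. With 3 deaths and 2 unknown, the true proportion alive in the set lies between 80.8% and 88.5%. The planned figure is the lower bound, and Kaplan-Meier lands near the upper one only by assuming that loss is uninformative, which is unverified in relapsed disease.

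The per protocol set narrows the effect. If these outcomes count as efficacy, a patient lost before any efficacy assessment after baseline leaves numerator and denominator together (SAP 3.3), so the effect concerns later losses.

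Finally, activity is judged primarily by clonal response (protocol 19.1), and no test or threshold uses these rates.

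What does not stand is that the plan already covers the point. The Kaplan-Meier option is for progression curves only and does not replace the 6-month figure. The optional sensitivity analysis in SAP section 3 is triggered by a difference in analysis-set sizes, not by missing 6-month status.

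**Conclusion.** The point holds as a low-priority defect in a stated rule. SAP 5.1 and 5.3.2 together make each patient of unknown 6-month status lower both rates as an event would, by 3.8 points at an assumed n of 26. The size rests on assumed deaths and losses and is zero if follow-up is complete.

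A reader might infer more: that the trial will publish two contradictory results, with a lost patient counted as not alive in one and not dead in the other. The documents do not support that. SAP 5.3.2 tabulates patients alive and plans no separate death table. The death count appears only as the name of the endpoint, and a count of known deaths says nothing about the remaining patients. What is left is a mismatch between the endpoint as listed and the analysis as planned.

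Nor do the documents show that Kaplan-Meier is the true value and the crude rate simply wrong. The crude rate is a worst-case bound that the plan presents, unlabelled, as the estimate.

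**What to change.** In SAP 5.3.2 (secondary endpoints):

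- Make the 6-month overall survival and progression-free survival figures Kaplan-Meier estimates with 90% and 95% log-log intervals. Censor at the last date known alive for survival and at the last disease assessment for progression-free survival.
- Beside each, give the numbers with an event (dead; progressed or dead), known to be event-free, and unknown at 6 months.
- Keep the crude proportion, labelled as the bound that treats every unknown as an event.

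In SAP 2.2 and 2.3.2, align the mortality endpoint with this analysis and define progression free at 6 months.

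The cost is mainly SAP text, with no change to patients, visits or sample size. It is not wholly free: neither the key data items in SAP 4.2 nor the assessment table in protocol 11.0 lists a last-known-alive date, so it would have to be derived from visit and withdrawal records. Kaplan-Meier also brings the assumption that losses are uninformative, which is why the crude bound and the unknown count should stay in the table. If nobody is lost, the point estimates are unchanged.
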